### If dosed under high fat meal condition in PART-1 or PART-3:

• Following an overnight fast of at least 10 hours, participants should start a high-fat/high-calorie breakfast approximately 30 minutes prior to administration of the investigational product. The breakfast will be consumed over approximately

20 minutes with investigational product administered within approximately 10 minutes after completion of the meal. Participants will be encouraged to eat the full meal. If participants are unable to complete the entire meal, the approximate portion of the meal consumed will be documented. No food will be allowed for at least 2 hours post-dose.

- The breakfast will be a high-calorie/high-fat test meal. The test meal should derive approximately 150, 250 and 500-600 calories from protein, carbohydrate and fat, respectively. The following breakfast as a representative example of a high-fat, high-calorie meal: 2 eggs fried in butter, 2 strips of bacon, 2 slices of toast with butter, 4 ounces of hash brown potatoes, 8 fluid ounces (240 mL) of whole milk.
- Water can be allowed as desired except for 1 hour after investigational product administration. There are no water restrictions prior to dosing for participants dosed under fed conditions.

#### If dosed under standard meal condition in PART-2:

## Morning dosing condition:

Following an overnight fast of at least 7 hours, participants should start a standard breakfast approximately 30 minutes prior to the morning administration of the investigational product. The breakfast will be consumed over approximately 20 minutes with investigational product administered within approximately 10 minutes after completion of the meal. Participants will be encouraged to eat the full standard breakfast. If participants are unable to complete the entire breakfast on PK profile assessment days (Days 1, 5 and 10), the approximate portion of the breakfast consumed will be documented. On non-PK days, it is not required to document the approximate portion of food consumed. No food will be allowed for at least 2 hours post-dose.

Water can be allowed as desired except for 1 hour after investigational product administration on PK days. There are no water restrictions on non-PK days neither prior to dosing for participants dosed under fed conditions.

#### Afternoon and/or evening dosing condition:

A snack consisting of at least 400 kcal will be provided approximately 20 minutes before dosing in the afternoon and/or evening. The snacks will be consumed over approximately 10 minutes with investigational product administered within approximately 10 minutes after completion of the snack. Participants will be encouraged to eat the full snack. There is no food restrictions on afternoon and/or evening dose(s).

There are no water restrictions on afternoon and/or evening dose(s) on PK days and on non-PK days.

## 5.3.1.1. Dietary Fiber Supplementation (PART-4 and PART-5 only)

To help assure regularity in bowel movements, nutritional composition should include high fiber content. This may include consumption of fiber capsules, at a frequency dictated by investigator, starting with the evening meal (ie, approximately 8 or 9 hours post dose) on Day 1, for duration of inpatient stay to ensure at least 1 bowel movement per day.

If an individual participant has not experienced a bowel movement in the first 24 hours after dosing water intake should be increased and prune juice should be offered on Day 2.

Despite these measures, if bowel movement does not occur regularly (ie, at least once daily bowel movement), consideration should be given to administration of mild laxative/stool softener (eg, milk of magnesia or docusate), at investigator's discretion.

## 5.3.2. Caffeine, Alcohol, and Tobacco

- Participants will abstain from caffeine containing products for 24 hours prior to the start of dosing of PF-07321332/placebo until collection of the final PK sample of each study period.
- Participants will abstain from alcohol for 24 hours prior (or as specified above for red wine) to admission to the CRU and continue abstaining from alcohol until collection of the final PK sample of each study period. Participants may undergo an alcohol breath test or blood alcohol test at the discretion of the investigator.
- Participants will abstain from the use of tobacco or nicotine containing products for 24 hours prior to dosing of PF-07321332/placebo and during confinement in the CRU.

## 5.3.3. Activity

- Participants will abstain from strenuous exercise (eg, heavy lifting, weight training, calisthenics, aerobics) for at least 48 hours prior to each blood collection for clinical laboratory tests. Walking at a normal pace will be permitted.
- In order to standardize the conditions on PK sampling days, participants will be required to refrain from lying down (except when required for BP, pulse rate, respiratory rate and ECG measurements) for first 4 hours after morning dose, and may be required to follow meals and dietary restrictions as specified in Section 5.3.1.
- PART-1 and PART-5 only: Participants will be confined to the procedure room for the first 4 hours after last PF-07321332/placebo dosing on Day 1 during continuous cardiac monitoring, except to use the bathroom. After this, if the equipment setup allows, participants may be ambulatory during the ECG monitoring period, but should not engage in strenuous activities. If equipment does not allow ambulation, appropriate accommodations will be made by the investigator site to facilitate continuous monitoring (eg, bedside urinals should be provided to accommodate participants' excretory needs).

PFIZER CONFIDENTIAL

## **5.3.4.** Contraception

The investigator or his or her designee, in consultation with the participant, will confirm that the participant has selected an appropriate method of contraception for the individual participant and his or her partner(s) from the permitted list of contraception methods (see Appendix 4 Section 10.4.4) and will confirm that the participant has been instructed in its consistent and correct use. At time points indicated in the SoA, the investigator or designee will inform the participant of the need to use highly effective contraception consistently and correctly and document the conversation and the participant's affirmation in the participant's chart (participants need to affirm their consistent and correct use of at least 1 of the selected methods of contraception). In addition, the investigator or designee will instruct the participant to call immediately if the selected contraception method is discontinued or if pregnancy is known or suspected in the participant or partner.

#### 5.4. Screen Failures

Screen failures are defined as participants who consent to participate in the clinical study but are not subsequently randomly assigned to study intervention/enrolled in the study. Screen failure data are collected and remain as source and are not reported to the clinical database.

Individuals who do not meet the criteria for participation in this study (screen failure) may be rescreened.

#### 6. STUDY INTERVENTION

Study intervention is defined as any investigational intervention(s), marketed product(s), placebo, medical device(s), or study procedure(s) intended to be administered to a study participant according to the study protocol.

For the purposes of this protocol, study intervention refers to all of the following:

- PF-07321332;
- Placebo for PF-07321332;
- Ritonavir.

## 6.1. Study Intervention(s) Administered

PF-07321332 and placebo will be provided by Pfizer as bulk powders for extemporaneous preparation of oral suspensions at the CRU.

PF-07321332 or placebo will be presented to the participants in individual dosing containers.

In addition, PF-07321332 and matching placebo may also be supplied as tablets. If provided, tablets will be supplied to the CRU in bulk along with individual dosing containers for unit dosing.

Ritonavir 100 mg tablets will be supplied locally by the CRU.

#### 6.1.1. Administration

Dosing of PF-07321332/placebo (placebo for PART-1 only) and ritonavir (if used) in PART-1 and PART-3

If dosed under fasted condition, participants will receive PF-07321332/placebo (placebo for PART-1 only) at approximately 08:00 hours (±2 hours) per the SoA following an overnight fast of at least 10h. In PART-1, if required, 3 doses of 100 mg ritonavir may be administered as a PK boosting agent as per SoA. At a time point when PF-07321332/placebo (placebo for PART-1 only) will be dosed with ritonavir (ie, at 0h), both PF-07321332/placebo (placebo for PART-1 only) and ritonavir will be dosed simultaneously (within no more than 5 minutes of each other). Participants will swallow ritonavir and PF-07321332/placebo (placebo for PART-1 only) tablets whole (if administered as tablet) and will not chew prior to swallowing.

Investigator site personnel will administer with ambient temperature water to a total volume of approximately 240 mL. Study intervention will be administered according to the EDR.

If dosed under fed condition (standard meal or high-fat high-calorie meal), the PF-07321332/placebo (placebo for PART-1 only) should be administered approximately 10 minutes after finishing the meal/snack (refer Section 5.3.1 for further details).

## Dosing of PF-07321332/placebo and ritonavir (if used) in PART-2

If dosed under fasted condition, participants will receive PF-07321332/placebo at approximately 08:00 hours (plus or minus 2 hours) per the SoA following an overnight fast of at least 7 hours. At least 2h of fast is required for afternoon and/or evening dosing for BID and TID dosing regimen. When dosed with ritonavir, both PF-07321332/placebo and ritonavir will be dosed simultaneously (within no more than 5 minutes of each other). Participants will swallow ritonavir and PF-07321332/placebo tablets whole (if administered as tablet) and will not chew prior to swallowing.

Investigator site personnel will administer with ambient temperature water to a total volume of approximately 240 mL. Study intervention will be administered according to the EDR.

If dosed under fed condition (meal/snack), the PF-07321332/placebo should be administered approximately 10 minutes after finishing the meal/snack (refer Section 5.3.1 for further details).

## Dosing of PF-07321332 and ritonavir in PART-4

Participants will receive PF-07321332 and ritonavir at approximately 08:00 hours (±2 hours) per the SoA following an overnight fast of at least 10h. Participants will receive 4 doses of 100 mg ritonavir as a PK boosting agent as per SoA. At a time point when PF-07321332 will be dosed with ritonavir (ie, at 0h), both PF-07321332 and ritonavir will be dosed

simultaneously (within no more than 5 minutes of each other) in fasted state. Except when dosed with PF-07321332, ritonavir may be administered with or without food. Participants will swallow ritonavir tablets whole and will not chew prior to swallowing.

Investigator site personnel will administer PF-07321332 oral suspension and ritonavir tablets with ambient temperature water to a total volume of approximately 240 mL. PF-07321332 oral suspension will be administered according to the EDR.

## Dosing of PF-07321332/placebo and ritonavir in PART-5

In this part, for each period, participants will receive split administrations (3 doses) of PF-07321332 or placebo at short intervals (within 2 h of the previous dose).

Participants will receive first split dose of PF-07321332/placebo oral suspension at approximately 08:00 hours (±2 hours) at least 2h after the morning breakfast per the SoA. The second and third split doses will be administered at approximately 2h and 4h after the first dose, respectively. A total of 3 doses of 100 mg ritonavir tablet will be administered as a PK boosting agent as per SoA. At a time point when PF-07321332/placebo will be dosed with ritonavir (ie, at 0h), both PF-07321332/placebo and ritonavir will be dosed simultaneously (within no more than 5 minutes of each other). Participants will swallow ritonavir tablets whole and will not chew prior to swallowing.

Investigator site personnel will administer with ambient temperature water to a total volume of approximately 240 mL. PF-07321332/placebo will be administered according to the EDR.

| Intervention Name   | PF-07321332  | Placebo   | Ritonavir (if used)   |
|--|--|---|---|
| ARM Name (group of patients receiving a specific treatment (or no treatment) | PF-07321332  | Placebo   | NA  |
| Туре   | Drug   | Placebo   | Boosting agent  |
| Dose Formulation   | Suspension or Tablet   | Suspension or Tablet  | Tablet  |
| Unit Dose Strength(s)  | Planned nominal unit
doses strength for
tablets: 25 mg, 100 mg,
and 250 mg  | 0 mg  | 100 mg  |
| Dosage Level(s)  | Planned nominal unit
doses strength for
tablets: 25 mg, 100 mg,
and 250 mg  | 0 mg  | 100 mg  |
| Route of
Administration   | Oral   | Oral  | Oral  |
| Use  | Experimental   | Placebo   | PK Boosting agent   |
| IMP or NIMP  | IMP  | IMP   | NIMP  |
| Sourcing   | Provided centrally by the sponsor  | Provided centrally by the sponsor   | Provided locally by the trial site, subsidiary, or designee |
| Packaging and Labeling   | Materials (API and components) for extemporaneous prep of oral suspensions will be provided in bulk. Tablets will be provided in bulk. PCRU staff will prepare individual doses for administration. Individual dose containers will be labeled by site staff per country requirement | Materials for extemporaneous prep of oral suspensions will be provided in bulk. Tablets will be provided in bulk. PCRU staff will prepare individual doses for administration. Individual dose containers will be labeled by site staff per country requirement | PCRU will procure commercially labeled materials            |
| Current/Former
Name(s) or Alias(es)                                       | PF-07321332  | Placebo   | Norvir® or other local commercialized product               |

## 6.2. Preparation/Handling/Storage/Accountability

- 1. The investigator or designee must confirm appropriate temperature conditions have been maintained during transit for all study interventions received and any discrepancies are reported and resolved before use of the study intervention.
- 2. Only participants enrolled in the study may receive study intervention and only authorized site staff may supply or administer study intervention. All study interventions must be stored in a secure, environmentally controlled, and monitored (manual or automated recording) area in accordance with the labeled storage

conditions with access limited to the investigator and authorized site staff. At a minimum, daily minimum and maximum temperatures for all site storage locations must be documented and available upon request. Data for nonworking days must indicate the minimum and maximum temperatures since previously documented for all site storage locations upon return to business.

- 3. Any excursions from the study intervention label storage conditions should be reported to Pfizer upon discovery along with any actions taken. The site should actively pursue options for returning the study intervention to the storage conditions described in the labeling, as soon as possible. Once an excursion is identified, the study intervention must be quarantined and not used until Pfizer provides permission to use the study intervention. Specific details regarding the definition of an excursion and information the site should report for each excursion will be provided to the site in the PCRU site procedures.
- 4. Any storage conditions stated in the SRSD will be superseded by the storage conditions stated on the label.
- 5. Study interventions should be stored in their original containers.
- 6. See the EDR for storage conditions of the study intervention once prepared.
- 7. The investigator, institution, or the head of the medical institution (where applicable) is responsible for study intervention accountability, reconciliation, and record maintenance (ie, receipt, reconciliation, and final disposition records), such as the IPAL or sponsor-approved equivalent. All study interventions will be accounted for using a study intervention accountability form/record.
- 8. Further guidance and information for the final disposition of unused study interventions are provided in the PCRU's site procedures. All destruction must be adequately documented. If destruction is authorized to take place at the investigator site, the investigator must ensure that the materials are destroyed in compliance with applicable environmental regulations, institutional policy, and any special instructions provided by Pfizer.

Upon identification of a product complaint, notify the sponsor within 1 business day of discovery.

#### 6.2.1. Preparation and Dispensing

Within this protocol, preparation refers to the investigator site activities performed to make the study intervention ready for administration or dispensing to the participant by qualified staff. Dispensing is defined as the provision of study intervention, concomitant treatments, and accompanying information by qualified staff member(s) to a healthcare provider, participant in accordance with this protocol. Local health authority regulations or investigator site guidelines may use alternative terms for these activities.

PF-07321332 and placebo oral dosing suspensions will be prepared in the CRU by 2 operators, 1 of whom is a pharmacist. Details of dose preparation will be given in a separate EDR. Prepared doses will be provided in unit dose containers and labeled in accordance with Pfizer regulations and the investigator site's labeling requirements.

PF-07321332 and placebo tablets, if used, will be dispensed at the CRU in the individual dosing containers by 2 operators, 1 of whom is an appropriately qualified and experienced member of the study staff (eg, physician, nurse, physician's assistant, nurse practitioner, pharmacy assistant/technician, or pharmacist). The tablets will be provided in unit dose containers and labeled in accordance with Pfizer regulations and the clinical site's labeling requirements.

Ritonavir will be administered to the participant in an unblinded (open-label) fashion. Ritonavir tablets will be dispensed at the CRU in the individual dosing containers by 2 operators, 1 of whom is an appropriately qualified and experienced member of the study staff (eg, physician, nurse, physician's assistant, nurse practitioner, pharmacy assistant/technician, or pharmacist). The tablets will be provided in unit dose containers and labeled in accordance with Pfizer regulations and the clinical site's labeling requirements.

## 6.3. Measures to Minimize Bias: Randomization and Blinding

## **6.3.1.** Allocation to Study Intervention

The investigator will assign participant numbers to the participants as they are screened for the study. Pfizer will provide a randomization schedule to the investigator and, in accordance with the randomization numbers, the participant will receive the study treatment regimen assigned to the corresponding randomization number.

Investigators and participants will remain blinded to each participant's assigned study intervention throughout the course of the study. In order to maintain this blind, an otherwise uninvolved third party (for example, pharmacist) will be responsible for the preparation and dispensing of all study intervention according to the randomization schedule and assigned treatment for the individual participant.

This third party will instruct the participant to avoid discussing the taste, or packaging of the study intervention with the investigator.

Blinding procedures do not apply to PART-3 and PART-4 of this study because it will be conducted as open-label. Where the design is open-label, the investigator's knowledge of the treatment should not influence the decision to enroll a particular participant or affect the order in which participants are enrolled.

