## 3. OBJECTIVES AND ENDPOINTS

## PART-1: SAD

| Objectives   | Endpoints   |  |  |
|--|---|--|--|
| Primary:   | Primary:  |  |  |
| To assess the safety and tolerability following a single dose of PF-07321332 alone or in combination with a PK boosting agent (ritonavir).                               | 
 
Frequency, severity, and causal relationship of TEAEs and withdrawals due to TEAEs.
 
Frequency and magnitude of abnormal laboratory findings.
 
Changes from baseline in vital sign measurements and 12-lead ECG parameters.
 
                   |  |  |
| Secondary:   | Secondary:  |  |  |
| To assess the plasma PK profile of
PF-07321332 following single ascending
doses of PF-07321332 alone or in
combination with a PK boosting agent
(ritonavir). | 
 
Plasma PK parameters of PF-07321332:
 
Cmax, Tmax, AUClast, Cmax(dn), AUClast(dn).
 
If data permit, AUCinf, AUCinf(dn), t½, Vz/F, and CL/F.
 
 |  |  |
| Tertiary/Exploratory:  | Tertiary/Exploratory:   |  |  |
| To explore metabolites in plasma, urine, and feces, if data permit.  | Qualitative characterization of metabolites of PF-07321332 in pooled plasma, urine, and feces if data permit.   |  |  |
| Quantitative excretion of drug-related
material using  F-NMR spectroscopy, if
data permit.  | Total excretion of drug-related material in urine and feces separately, and both routes combined, expressed as a percent of total dose administered, if data permit.  |  |  |
| To determine the oral bioavailability of a tablet formulation of PF-07321332 relative to suspension, if evaluated (Optional).  | The ratio of AUC last , AUC inf and C max of tablet formulation and suspension.  |  |  |
| To evaluate the effect of food (high fat meal) on the exposure of PF-07321332 following a single oral dose of PF-07321332 tablet formulation, if evaluated (Optional).   | The ratio of AUC last , AUC inf and C max under fed condition and fasted condition.  |  |  |

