### 8.3. Adverse Events and Serious Adverse Events

The definitions of an AE and an SAE can be found in Appendix 3.

AEs will be reported by the participant (or, when appropriate, by a caregiver, surrogate, or the participant's legally authorized representative).

The investigator and any qualified designees are responsible for detecting, documenting, and recording events that meet the definition of an AE or SAE and remain responsible to pursue and obtain adequate information both to determine the outcome and to assess whether the event meets the criteria for classification as an SAE or caused the participant to discontinue the study intervention (see Section 7.1).

Each participant will be questioned about the occurrence of AEs in a nonleading manner.

In addition, the investigator may be requested by Pfizer Safety to obtain specific follow-up information in an expedited fashion.

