### 8.3.1.2. Recording Nonserious AEs and SAEs on the CRF

All nonserious AEs and SAEs occurring in a participant during the active collection period, which begins after obtaining informed consent as described in Section 8.3.1, will be recorded on the AE section of the CRF.

The investigator is to record on the CRF all directly observed and all spontaneously reported AEs and SAEs reported by the participant.

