## 8.3.2. Method of Detecting AEs and SAEs

The method of recording, evaluating, and assessing causality of AEs and SAEs and the procedures for completing and transmitting SAE reports are provided in Appendix 3.

Care will be taken not to introduce bias when detecting AEs and/or SAEs. Open-ended and nonleading verbal questioning of the participant is the preferred method to inquire about AE occurrences.

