## 10.3. Appendix 3: Adverse Events: Definitions and Procedures for Recording, Evaluating, Follow-up, and Reporting

#### 10.3.1. Definition of AE

#### **AE Definition**

- An AE is any untoward medical occurrence in a patient or clinical study participant, temporally associated with the use of study intervention, whether or not considered related to the study intervention.
- NOTE: An AE can therefore be any unfavorable and unintended sign (including an abnormal laboratory finding), symptom, or disease (new or exacerbated) temporally associated with the use of study intervention.

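### The blinding instruction not to discuss taste has no exception for taste symptoms and may discourage their reporting in PART-1, PART-2 and PART-5

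*Protocol*

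**What the plan says.** Protocol Section 6.3.1 gives preparation and dispensing to an otherwise uninvolved third party and adds: "This third party will instruct the participant to avoid discussing the taste, or packaging of the study intervention with the investigator". The same section limits its reach: "Blinding procedures do not apply to PART-3 and PART-4 of this study because it will be conducted as open-label". The instruction therefore applies to PART-1, PART-2 and PART-5.

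On adverse events, Section 8.3 states "AEs will be reported by the participant" (with provision for a caregiver or representative) and "The investigator and any qualified designees are responsible for detecting, documenting, and recording events that meet the definition of an AE or SAE". It also requires that each participant be questioned in a nonleading way. Section 8.3.2 adds: "Open-ended and nonleading verbal questioning of the participant is the preferred method to inquire about AE occurrences". Section 8.3.1.2 sets the recording duty: "The investigator is to record on the CRF all directly observed and all spontaneously reported AEs and SAEs reported by the participant". Appendix 3 (10.3.1) defines the event: "An AE is any untoward medical occurrence in a patient or clinical study participant, temporally associated with the use of study intervention". Its note extends this to unfavourable and unintended symptoms.

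Section 3 lists "Frequency, severity, and causal relationship of TEAEs and withdrawals due to TEAEs" among the primary endpoints of PART-1, with the same entry for PART-2 and PART-5. Section 9.4.2 confirms that the primary endpoints of those three parts concern safety and tolerability.

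**The concern.** One rule asks participants not to raise a subject with the investigator. The other relies on them to raise it. Section 6.3.1 does not separate the taste of the product, which could reveal allocation, from a taste disturbance felt afterwards, which is a symptom. To someone who has just swallowed a suspension, a lingering bitter or metallic taste is naturally the taste of the drug.

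At stake is the completeness of one class of event within a primary endpoint. Any loss from this source lowers the count. Groups are small (4 active per dose level in PART-1 and per cohort in PART-2, up to 12 participants in PART-5), so a single withheld report is visible in the observed frequency. SAP Section 6.6.1 reports AEs by sponsor standards, and no analysis can recover a complaint that was never voiced.

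**Working it through.** The plan has no figure on this point, so there is nothing to reproduce. The check is a reading of the provisions side by side, followed by an illustration.

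**Provisions compared**

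1. Scope. The instruction covers the blinded parts, PART-1, PART-2 and PART-5. These are the parts in which TEAEs are a primary endpoint.
2. Is a taste symptom an AE? Nothing in Appendix 3 excludes it. SAP Section 3.5.1 flags TEAEs by start time only, so such an event would count if recorded.
3. Does the collection method offset the instruction? Nonleading questioning is required, and open-ended questioning is preferred. Neither supplies a prompt about taste.
4. Is there another route? Qualified designees share AE collection under Section 8.3, and the instruction names only the investigator. The available text does not direct taste complaints to a designee.
5. Breadth. Section 6 counts ritonavir as study intervention, and Section 6.2.1 says it is given open-label. Read literally, the instruction also covers the taste of ritonavir, where no allocation is hidden.

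**Illustration (assumed inputs, not estimates)**

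Let n be the number of participants on active drug, p the true incidence of a reportable taste event and r the fraction of such events that is reported. Then

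P(at least one recorded) = 1 − (1 − p·r)^n.

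The value n = 4 comes from Sections 9.2.1 and 9.2.2. The value n = 12 is the PART-5 maximum in Section 9.2.5, where the crossover gives each participant an active period. Both p and r are assumptions, and both are varied.

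Worked case, n = 4 and p = 0.25:

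- r = 1: 1 − 0.75^4 = 0.68
- r = 0.75: 1 − 0.8125^4 = 0.56
- r = 0.50: 1 − 0.875^4 = 0.41
- r = 0.25: 1 − 0.9375^4 = 0.23

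| n | p | r = 1 | r = 0.75 | r = 0.50 | r = 0.25 |
|---|---|---|---|---|---|
| 4 | 0.10 | 0.34 | 0.27 | 0.19 | 0.10 |
| 4 | 0.25 | 0.68 | 0.56 | 0.41 | 0.23 |
| 4 | 0.50 | 0.94 | 0.85 | 0.68 | 0.41 |
| 12 | 0.10 | 0.72 | 0.61 | 0.46 | 0.26 |
| 12 | 0.25 | 0.97 | 0.92 | 0.80 | 0.54 |
| 12 | 0.50 | 1.00 | 1.00 | 0.97 | 0.80 |

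The r = 1 column is the case of no effect. One unreported event moves the observed frequency by 1/4 = 25 percentage points in a group of 4, and by 1/12 = 8.3 points in a group of 12.

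**The case against.** The strongest reply is that the instruction concerns the product. Taste is paired with packaging, and both are features that could reveal allocation. Symptoms are not mentioned, and the duties to question participants and record every reported AE are untouched. That is the more natural reading, and it stands as an account of intent. It does not remove the gap, because the instruction is addressed to lay participants and does not draw the line for them.

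Other replies also carry weight:

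- Designees collect AEs too, so the investigator is not the only channel. This is correct, though participants are not told to use the other one.
- Safety is summarised descriptively, with no hypothesis test. The specific stopping criteria in Section 6.6.1 turn on laboratory, ECG and vital-sign abnormalities, severe AEs, SAEs and exposure limits. A mild taste complaint would not by itself meet them, so no particular escalation decision is shown to be affected.
- The participant instructions and consent pages are not in the material available, and some assessments are redacted. One of these may already cover taste.
- A taste report may hint at allocation to the blinded investigator, who also rates intensity and causality. This is a real cost of any change.

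A reader might go further and infer that taste disturbance is in fact under-reported, or that the active-placebo difference is therefore reduced. The documents do not support either step. No provision shows that a report was or will be withheld. The direction of any effect on the contrast depends on taste complaints being commoner on active drug, which is not stated. In ritonavir-boosted cohorts both arms receive open-label ritonavir, so its taste effects would arise in both.

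**Conclusion.** The point holds as a possible source of under-reporting. In PART-1, PART-2 and PART-5 the instruction in Section 6.3.1 lacks an exception for taste-related symptoms and may discourage participants from reporting events that would count toward the primary TEAE endpoint. Its size is unknown and could be zero, since the documents give neither an incidence nor a reporting fraction. The probabilities above show only how sensitive small groups would be if some reports were withheld.

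A reader might also infer that AE profiles become non-comparable between the blinded and open-label parts. That does not follow as a defect of the plan. Protocol Section 9.4.1 and SAP Section 6 analyse and report each part separately, and no cross-part AE comparison is planned. This is a cheap improvement in wording that removes a possible bias; it does not put the design in question.

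**What to change.** Keep the restriction in Section 6.3.1 on commenting on the taste or packaging of the product. Add one sentence there and in the participant instructions, for example: Any altered, unpleasant or lasting taste, or any other symptom felt after dosing, should be reported to the investigator or a qualified designee in the same way as any other symptom.

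Each report should then be assessed against the AE definition in Appendix 3, not recorded automatically as an AE. That keeps a remark about flavour apart from a symptom.

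The cost is one sentence in two places, with no change to sample size, schedule or analysis. The downside is that a reported taste symptom may hint at allocation. Section 8.3.1.2 already accepts that risk, because it requires every spontaneously reported AE to be recorded. Allowing the report to go to a designee may limit what reaches the person rating causality.
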